- Triplet 12-lead ECG recordings with 2-minute intervals ( $\pm 1$  minute) after at least 5 minutes rest in supine position at predose (within 60 minutes prior to dose) and 4 hours ( $\pm 12$  minutes) postdose. ECGs should be performed within 10 minutes prior to PK sampling at time points where both assessments are performed
- PK blood samples. Samples will be taken predose (within 60 minutes prior to dose) and at 0.25, 0.5, 1, 2, 4, 8, 10, and 24 hours postdose. Note: the 24-hour postdose sample from Day 1 and Day 15 are the predose samples from Day 2 and Day 16, respectively. Postdose PK samples should be taken within  $\pm 5\%$  of the scheduled assessment time, e.g., the 4-hour postdose sample should be obtained at 4 hours  $\pm 12$  minutes
- CCI [REDACTED]
- CCI [REDACTED]

The following assessments will be performed only if screening/last assessments were performed > 7 days prior to Day 1:

- ECOG PS
- Urinalysis (dipstick followed by microscopic examination if abnormal results)
- Serum AFP

Assessments for Cycle 1, Day 1 of Phase II include all assessments in Phase Ib with the following changes:

- Randomization by IVRS
- PK blood samples. Samples will be taken predose (within 60 minutes prior to dose) and 4 hours postdose in the MSC2156119J arm. At selected sites, PK sampling will be performed predose (within 60 minutes prior to dose) and at 1.5, 3.5, and 6.5-8 hours postdose. Postdose PK samples should be taken within  $\pm 5\%$  of the scheduled assessment time, e.g., the 4-hour postdose sample should be obtained at 4 hours  $\pm 12$  minutes
- FHSI-8
- PRO (FACT-HP) (see [Appendix G](#))

### 8.1.3.2 Cycle 1, Day 15

On Cycle 1, Day 15 of Phase Ib, the following assessments/treatment administrations will occur:

- Tumor biopsy (excluding fine needle aspiration and cytology samples). Undergoing paired tumor biopsy is not mandatory, but highly recommended for subjects with accessible tumors: the paired tumor biopsy will be performed before treatment at screening or on Cycle 1, Day 1 and anytime between Cycle 1, Day 15 and beginning of Cycle 3 (optional, will be collected after subjects have signed a separate ICF). A predose PK is recommended to be taken on the day of the second biopsy.

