Assessments for Cycle 2, Day 15 of Phase Ib will be the same as the assessments for Cycle 1, Day 15, as defined in Section 8.1.3.2, except for tumor biopsy, vital signs, 12-lead ECG, and PK blood samples.

#### 8.1.3.5 Cycles $\geq 3$ , Day 1

Assessments for Cycles  $\geq 3$ , Day 1 of Phase Ib include all assessments from Cycle 1, Day 1, except a tumor biopsy will not be taken, and CCI blood samples will not be drawn. CCI

In addition, a complete tumor assessment of all lesions by radiographic or other modality (using RECIST v 1.1) identified at the screening visit will be performed predose on, or up to 5 days prior to, Day 1 of Cycles 3, 5, 7, 9, 11, 13, and every 4 cycles thereafter until disease progression, starting a new anti-tumor therapy, or death.

Assessments for Cycles  $\geq 3$ , Day 1 of Phase II include all Cycles  $\geq 3$ , Day 1 assessments in Phase Ib.

In addition, HBV DNA, HBV serology, and HCV RNA-PCR will be monitored every 3 cycles according to the subject's baseline status and previous HBV/HCV history (see Section 7.5.3.1), FHSI-8 will be assessed, FACT-HP will be assessed on Cycle 5, Day 1.

CCI

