Abbreviations: AFP, alpha-fetoprotein; ALT, alanine aminotransferase; aPTT, activated partial thromboplastin time; AST, aspartate aminotransferase; BUN, blood urea nitrogen; CNS, central nervous system; CT, computed tomography; ECG, electrocardiogram; ECOG PS, Eastern Cooperative Oncology Group performance status; EoT, end of treatment; CCI; gamma-glutamyl transpeptidase; HBc, hepatitis B core antigen; HBsAg, hepatitis B e antigen; HBsAg, hepatitis B surface antigen; HBV, hepatitis B virus; HCC; hepatocellular carcinoma; HCV, hepatitis C virus; ICF, Informed Consent Form; INR, international normalized ratio; IVRS; interactive voice response system; RECIST, response evaluation criteria in solid tumors; MRI, magnetic resonance imaging; CCI; CCI; PRO, subject reported outcomes; PT, prothrombin time; RNA, ribonucleic acid.

- a All visits and assessments from Cycle 2 onwards may be performed +/- 5 days to accommodate unforeseen delays, holidays, or vacations.
- b End of treatment visit, performed on the last day of treatment, whether at the end of a cycle or not. The last day of treatment is defined as the day on which it is determined that the subject will no longer receive the study drug.
- c Post-treatment follow-up visit, performed within 30 ± 3 days after the last treatment for all subjects who discontinue trial treatment permanently, including subjects who have completed an end of treatment visit.
- d Survival data will be collected every 3 months after end of treatment until death or the end of the trial.

- e MET status will be confirmed during Molecular Prescreening after the subject has signed the prescreening ICF. Demographic data and disease history will also be collected during Molecular Prescreening once the subject has signed the main ICF. Clinical Screening will include laboratory parameters, medical history and all other assessments needed to confirm subject eligibility, plus demographic data and disease history if not already collected. Clinical Screening assessments must be completed within 14 days prior to the initiation of study treatment. MET status rescoring will be performed as a quality control measure; subjects with a MET status of 1+ or 'not assessable' on rescoring will be excluded from the modified intent-to-treat population.

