- x To be performed predose on, or within 5 days prior to, Day 1 of Cycles 3, 5, 7, 9, 11, 13, i.e., at 6-week intervals, and every 4 cycles thereafter, i.e., at 12-week intervals, until disease progression, starting a new anti-tumor therapy, or death. The scheduled 6-week (or 12 week) interval between tumor response assessments should be maintained through the trial regardless of any delay or interruption to trial treatment.
- y If a subject discontinues trial treatment for a reason other than disease progression or death, tumor assessment will be performed at EoT if it has not been done within the past 6 weeks, and will be repeated every 6 weeks ( $\pm$  1 week) until radiological progression per RECIST v 1.1, death or start of new anticancer therapy, whichever occurs first.

[REDACTED]

CCI

CCI

dd On Cycle 5, Day 1 and the end of treatment visit (only if the subject discontinued before Cycle 5, Day 1).

[REDACTED]

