Secondary endpoint(s)	
Secondary efficacy endpoints are:
 
• Progression-free survival (PFS) assessed by investigator. PFS time is defined as the time (in months) from first administration to either first observation of disease progression or occurrence of death due to any cause within 84 days of either first administration or the last tumor assessment.• Overall survival (OS) time. OS time is defined as the time (in months) from first administration to the date of death.• TTP assessed by investigator. TTP is defined as the time (in months) from first administration to date of the observation of radiological PD assessed by the investigator.• Objective response (OR). OR is defined as complete response (CR) or partial response (PR) as the best overall response according to local radiological assessments from first administration to first occurrence of PD. Responses do not require confirmation according to RECIST v 1.1.• Disease control. Disease control is defined as CR, PR, or stable disease (SD) as the best overall response according to local radiological assessments from the date of first administration to the first occurrence of PD. In the case of SD, measurements must have met the SD criteria at least once after study entry at a minimum interval of 42 days after first administration. 
Secondary safety endpoints are:
 
• Drug exposure.• Incidence and type of AEs (all grades as per the National Cancer Institute's (NCI)-CTCAE version 4.0): all treatment emergent adverse events (TEAEs), related TEAEs, treatment emergent serious adverse events (SAEs), related treatment emergent SAEs, TEAEs of NCI-CTCAE (version

	
4.0) with Grade \geq 3, related TEAEs \geq Grade 3, and TEAEs leading to permanent/temporary treatment discontinuation.
 
 • Incidence and reasons for deaths, including deaths within 33 days after the last dose of study drug. • Safety laboratory tests graded by NCI-CTCAE (version 4.0). • Vital signs; 12-lead ECG changes; physical examinations, including change in body weight; and ECOG PS.

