- median, 25th Percentile - 75th Percentile (Q1-Q3),
- minimum, and maximum,

CCI

Categorical variables will be summarized by counts and percentages.

Unless otherwise stated the calculation of proportions will be based on the number of patients of the sample size of the population of interest. Therefore counts of missing observations will be included in the denominator and presented as a separate category.

Trial day and treatment day:

Trial day is defined relative to the date of randomization. Day 1 is defined as the day of the randomization, the day before is defined as Trial day -1 (no Trial day 0 is defined).

- Trial day =
 - date of event – the date of randomization, if date of event < the date of randomization
 - or date of event – the date of randomization + 1 , if date of event ≥ the date of randomization

Treatment day will be calculated relative to the date of the first administration of trial treatment, treatment day 1 is defined as the first administration day.

- Treatment day = date of event – first administration day + 1

In the situation where the event date is partial or missing, the date will appear partial or missing in the listings, and Trial Day or Treatment Day, and any corresponding durations will be presented as missing. Rules of handling missing dates relevant to efficacy will be specified in the subsequent sections.

Definition of baseline:

In general the last non-missing measurement prior to or on the day of randomization will serve as the baseline measurement. If such a value is not available, the last measurement prior to or on the day of the first trial treatment administration will serve as the baseline measurement.

If an assessment is planned to be performed prior to the first dose of study treatment in the protocol and the assessment is performed on the same day as the first dose of study treatment, it will be assumed that it was performed prior to study treatment administration, if assessment time point is not collected or is missing. If assessment time points are collected, the observed time point will be used to determine pre-dose on study day 1 for baseline calculation. Unscheduled assessments will be used in the determination of baseline. However, if time is missing, an unscheduled assessment on study day 1 will be considered to have been obtained after study treatment administration.

Definition of on-treatment value:

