On-treatment data refer to assessment values collected after the first trial drug administration of any trial treatment and within 33 days (inclusive) after the last trial drug administration.

End of treatment (EOT) data

Data reported at the EOT visit are not eligible for the baseline selection. EOT data will be presented in a separate visit in the by-visit summaries.

Unscheduled visits:

Generally, data collected at unscheduled visits will be included and analyzed for both safety and efficacy analyses in the same fashion as the data collected at scheduled visits except where otherwise noted in the sections that follow. Descriptive statistics (mean, SD, median, minimum, maximum, quartiles) by nominal visit or time point for safety endpoints such as laboratory measurements, ECGs and vital signs will include only data from scheduled visits.

Definition of duration:

Duration will be calculated by the difference between start and stop date + 1 if not otherwise specified. For example, survival time (days) = date of death - the date of randomization + 1.

Common calculations:

For quantitative measurements, change from baseline will be calculated as:

- Test Value at Visit X – Baseline Value

Conversion factors:

Unless specified, Conversion of days to months /years will be defined as:

- 1 month= 30.4375 days
- 1 year = 365.25 days

Handling of missing data:

For the derivation of new date variables the following rules will apply:

- Partial birth dates will be handled this way: day will be imputed as 15 if it is missing, and month imputed as June if missing. If both of day and month are missing, they will be imputed as July 1st. If year is missing then the date will not be imputed.
- For imputing missing parts of dates for the efficacy analyses the missing day in a date will be imputed as the 15th of the month, if month and year is documented. This includes also dates of start of follow-up therapy.
- In case the last administration date is incomplete the date of last administration will be taken from the Treatment Termination eCRF page.
- Incomplete AE-related dates will be handled as follows:
 - In case the onset date is missing completely or missing partially but the onset month and year, or the onset year are equal to the start of trial treatment then the onset date will be replaced by the minimum of start of trial treatment and AE resolution date.
 - In all other cases the missing onset day or missing onset month will be replaced by 1.

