The common Mantel-Haenszel odds ratio (OR) adjusted by strata and the corresponding 90% CIs using the variance formula for the log of the common odds ratio estimate will be presented. The odds ratio is defined as the odds of showing response with the investigational drug, divided by the odds of showing response with the control treatment, i.e. an odds ratio greater than one corresponds to a benefit of the investigational arm. The homogeneity of the odds ratio across strata will be checked by the Breslow-Day test, The null hypothesis of no association in any of the strata is tested against the alternative, which says that at least in one stratum there is an association between treatment effect and tumor response. Additional to the Mantel-Haenszel estimate, odds ratios per stratum are indicated with the corresponding exact confidence interval. The common odds ratio with no adjustment by strata and its 90% CI will be provided as well.

The ORR rate will be presented for each treatment group including the corresponding 90% Newcombe-Wilson CIs.

The best percent change (%) from baseline for the sum of longest diameters will be displayed in a waterfall plot.

Disease Control Rate (DCR) by IRC

The disease control rate is defined as the proportion of patients having achieved CR, PR, or stable disease (SD) as the BOR according to radiological assessments from randomization until end of trial treatment the first occurrence of PD. In the case of SD, measurements must have met the SD criteria at least once after study entry at a minimum interval of 42 days after randomization.

The DCR rate and its 90% Newcombe-Wilson CI will be calculated.

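### The 42-day minimum for stable disease has no tolerance, yet the scan window allows the first scan from day 37, so SD seen only on a compliant early scan is lost from the disease control rate (minor, secondary endpoint)

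*SAP*

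**What the plan says.** The Phase II SAP (Section 16.2.6, DCR by IRC) counts SD as disease control only if "measurements must have met the SD criteria at least once after study entry at a minimum interval of 42 days after randomization". The same condition stands in the protocol Synopsis and Sections 9.3.2 and 9.5.3.4, and in Phase II SAP Sections 6 and 16.2.7 (the latter for the investigator's assessment). None of these places gives a tolerance.

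The timing of the first scan is set elsewhere:

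- Protocol 8.1.3.5: the tumor assessment "will be performed predose on, or up to 5 days prior to, Day 1 of Cycles 3, 5, 7, 9, 11, 13".
- Protocol Appendix I, footnote x: "To be performed predose on, or within 5 days prior to, Day 1 of Cycles 3, 5, 7", and so on.
- Protocol 8.1.3.1 lists "Randomization by IVRS" among the Phase II procedures of Cycle 1 Day 1. The Appendix I schedule agrees. Cycles last 21 days.

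Four further rules bear on the day count:

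- Phase II SAP Section 11: "Duration will be calculated by the difference between start and stop date + 1 if not otherwise specified".
- The same section dates first dose separately from randomization: "Treatment day will be calculated relative to the date of the first administration of trial treatment".
- Appendix I, footnote a: "All visits and assessments from Cycle 2 onwards may be performed +/- 5 days".
- Protocol 8.3 and Appendix I, footnote w: a scheduled scan may be skipped if it falls within 14 days after unscheduled imaging that did not show progression.

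The Phase Ib SAP (Sections 6 and 16.2.4) has the same SD rule, "at a minimum interval of 42 days after first administration", and Appendix H, footnote v, has the same scan window.

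**The concern.** The SD threshold coincides with the last day of a scan window that opens only towards earlier dates. A site that follows the protocol exactly can produce a first scan that cannot support disease control. Take two patients with SD at the first scan and progression at the second, both scanned within the window, one on day 38 and one on day 42. The first is a DCR failure and the second a DCR success, and only the booking day separates them.

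DCR then measures control at about 6 weeks in some patients and at about 12 weeks in others. What is at stake is the level and the meaning of DCR, for the IRC and for the investigator.

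**Working it through.** **Reproducing the plan's figure.** Two cycles of 21 days give 2 × 21 = 42 days from Cycle 1 Day 1 to Cycle 3 Day 1. This is the stated minimum, so the rule is evidently meant to capture the week-6 scan.

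**Permitted scan days.** With randomization on Cycle 1 Day 1, the window is 42 − 5 = 37 to 42 days after randomization, six possible days.

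- Plain difference: days 37 to 41 miss the minimum (5 of 6).
- Difference plus one (the SAP default for durations): days 37 to 40 miss it (4 of 6).

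**Lag from randomization to first dose.** A lag of L days moves the window to 37 + L to 42 + L. Number of the six days that are too early:

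| Lag (days) | 0 | 1 | 2 | 3 | 4 | 5 |
|---|---|---|---|---|---|---|
| Plain difference | 5 | 4 | 3 | 2 | 1 | 0 |
| Difference plus one | 4 | 3 | 2 | 1 | 0 | 0 |

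A lag of 4 days (plus one) or 5 days (plain) removes the problem in Phase II. In Phase Ib the count starts at first dose, so no lag applies.

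**General visit window.** If footnote a also moves the scan, the range becomes 42 − 5 − 5 = 32 to 42 + 5 = 47 days. Then 10 of 16 days (plain) or 9 of 16 (plus one) are too early.

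**Size, as an illustration.** Inputs from protocol 9.1: median TTP 2.8 months on sorafenib, and 2.8 / 0.6 = 4.67 months on tepotinib. Conversion from SAP Section 11: 30.4375 days per month. Assumptions: exponential TTP, no responders, no drop-out, and day 42 used as an approximation for the earlier scan.

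- S(42 days) = exp(−ln 2 / median × 42 / 30.4375) = 0.711 (sorafenib) and 0.815 (tepotinib).
- Share with SD at week 6 and progression by week 12 = S × (1 − S) = 0.206 and 0.151.
- Fall in DCR = f × S × (1 − S), where f is the assumed share of first scans that are too early.

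| f | Sorafenib (points) | Tepotinib (points) |
|---|---|---|
| 0 | 0 | 0 |
| 2/6 | 6.9 | 5.0 |
| 4/6 | 13.7 | 10.1 |
| 5/6 | 17.1 | 12.6 |

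With scans spread evenly over the six days and no lag, f is 4/6 (plus one) or 5/6 (plain).

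**How rough this is.** For a scan on day 37 followed by one on day 79 to 84, the sorafenib share is 0.740 − 0.526 = 0.214 to 0.740 − 0.505 = 0.235, against the 0.206 used. Patients with no evaluable scan after an early SD scan would add to the loss; planning assumed 17.4% drop-out. Responders reduce it: if 10% of the affected group had CR or PR, f = 5/6 gives 0.9 × 17.1 = 15.4 and 0.9 × 12.6 = 11.3 points.

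**The case against.** **Six weeks is a legitimate, pre-specified choice.** Appendix C (Confirmation) leaves the minimum to the protocol and calls 6 to 8 weeks usual. Protocol 8.3 tells sites to keep the 6-week interval, and a scan on day 42 satisfies both rules. All of this stands. It means that 42 days is not an error and that 37 days need not become the sole definition. It does not remove the mismatch, because the schedule also permits the five earlier days.

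**The effect may be small or nil.** The value of f is unknown, a lag of 4 to 5 days removes the problem in Phase II, and the IRC charter, which is not among the documents, may specify how scans map to timepoints. These points stand too. They limit what can be said about size, and the charter would not settle the investigator's DCR.

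**A reader might infer that the treatment comparison is biased.** The documents do not support that. The rule is the same in both arms, and equal hazards give equal falls. At the planning medians the arm difference would move from 81.5 − 71.1 = 10.4 points at f = 0 to 68.9 − 53.9 = 15.0 at f = 5/6. The 90% CI half-width at those f = 5/6 rates is 1.645 × √[(0.539 × 0.461 + 0.689 × 0.311) / n], which is 16.7 points with 45 per arm and 17.7 with 40. Both sizes are assumptions based on about 90 randomized.

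**A reader might also infer that best overall response is undefined for these patients.** It is not. Protocol 9.3.1 ties the tumor endpoints to Appendix C, under which SD that misses the minimum and is followed by progression is PD, and SD followed by loss to follow-up is inevaluable.

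**Conclusion.** The mismatch is in the text and is certain, given randomization on Cycle 1 Day 1 as scheduled: the first scan may fall on days 37 to 42, and SD counts only from day 42. A compliant patient whose only SD is on an earlier scan is not counted in DCR.

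The size is not certain. It depends on f, which the documents do not give. Under the stated assumptions the fall runs from nil to 17.1 points (sorafenib) and 12.6 points (tepotinib) at f = 5/6. The upper figures should not be read as an expected loss.

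The point is minor. It affects the level and interpretability of one secondary endpoint in Phase II, and the same descriptive endpoint in Phase Ib. TTP, PFS, OS and ORR are untouched.

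**What to change.** Report DCR under two rules and name the main one in advance:

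- the strict 42-day rule as now written;
- a windowed rule, under which SD on the first scheduled assessment counts if the scan lies within its permitted window. That is from 42 − 5 = 37 days after randomization by plain difference, or 38 under difference plus one. In Phase Ib the count runs from first dose.

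State three things with it:

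- which day count applies;
- whether Appendix I, footnote a, also moves the scan. If it does, the earliest compliant scan is day 32 and the windowed minimum must match;
- how the windowed rule treats an unscheduled SD scan that replaces the week-6 scan under the 14-day provision. Such a scan could fall on day 42 − 14 = 28, so a 37-day minimum alone would not cover it.

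Apply this wherever the rule stands: protocol Synopsis, 9.3.2 and 9.5.3.4; Phase II SAP 6, 16.2.6 and 16.2.7; Phase Ib SAP 6 and 16.2.4. A cross-reference from the SAP definitions of best overall response is optional.

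The cost is wording in eight places and one extra DCR table, with no new data. The downside is that 37 days lies slightly below the 6 to 8 weeks that Appendix C calls usual. Keeping the strict result alongside covers that.

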16.2.7 Antitumor Activity Assessed by Investigator

Best overall response

BOR is defined as the best result obtained among all tumor assessment visits by investigator from baseline until end of treatment or determination of PD, excluding assessments after tumor surgery.

ORR based on tumor assessment by Investigator

OR based on tumor assessment by the investigator. OR is defined as CR or PR as the best overall response according to radiological assessments as adjudicated by the investigator from randomization to first occurrence of PD. Responses do not require confirmation according to RECIST v 1.1 (see Appendix C).

DCR based on tumor assessment by the investigator

Disease control is defined as CR, PR, or SD as the best overall response according to radiological assessments as adjudicated by the investigator from the date of randomization to the first occurrence of PD. In the case of SD, measurements must have met the SD criteria at least once after study entry at a minimum interval of 42 days after randomization.

